## 8.2 Adverse Event Characteristics

- **CTCAE term (AE description) and grade:** The descriptions and grading scales found in the revised NCI Common Terminology Criteria for Adverse Events (CTCAE) version 5.0 will be utilized for AE reporting. All appropriate treatment areas should have access to a copy of the CTCAE version 5.0. A copy of the CTCAE version 5.0 can be downloaded from the CTEP web site (<http://ctep.cancer.gov>).
- **‘Expectedness’:** AEs can be ‘Unexpected’ or ‘Expected’ (see Section 7.1 above) for expedited reporting purposes only.
- **Attribution** of the AE:
  - Definite – The AE is **clearly related** to the study treatment.
  - Probable – The AE is **likely related** to the study treatment.
  - Possible – The AE **may be related** to the study treatment.
  - Unlikely – The AE is **doubtfully related** to the study treatment.
  - Unrelated – The AE is **clearly NOT related** to the study treatment.

### **8.3 STRC SAE Reporting Requirements**

The Data Safety Monitoring Committee (DSMC) is responsible for reviewing SAEs for WFBCCC Institutional studies as outlined in Appendix B. All Adverse Events that occur during protocol intervention and are coded as either 1) unexpected grade 4, 2) unplanned inpatient hospitalization  $\geq$  24 hours (regardless of grade), or grade 5 (death) must be reported to the DSMC using the SAE console in WISER.

All WFBCCC Clinical Protocol and Data Management (CPDM) staff members assisting a Principal Investigator in investigating, documenting and reporting an SAE qualifying for DSMC reporting are responsible for informing a clinical member of the DSMC as well as the entire committee via the email notification procedure of the occurrence of an SAE.

### **8.4 WFUHS IRB AE Reporting Requirements**

Any unanticipated problems involving risks to subjects or others and adverse events shall be promptly reported to the IRB, according to institutional policy. Reporting to the IRB is required regardless of the funding source, study sponsor, or whether the event involves an investigational or marketed drug, biologic or device. Reportable events are not limited to physical injury, but include psychological, economic and social harm. Reportable events may arise as a result of drugs, biological agents, devices, procedures or other interventions, or as a result of questionnaires, surveys, observations or other interactions with research subjects.

All members of the research team are responsible for the appropriate reporting to the IRB and other applicable parties of unanticipated problems involving risk to subjects or others. The Principal Investigator, however, is ultimately responsible for ensuring the prompt reporting of unanticipated problems involving risk to subjects or others to the IRB. The Principal Investigator is also responsible for ensuring that all reported unanticipated risks to subjects and others which they receive are reviewed to determine whether the report represents a change in the risks and/or benefits to study participants, and whether any changes in the informed consent, protocol or other study-related documents are required.

Any unanticipated problems involving risks to subjects or others occurring at a site where the study has been approved by the WFUHS IRB (internal events) must be reported to the WFUHS IRB within 7 calendar days of the investigator or other members of the study team becoming aware of the event.

Any unanticipated problems involving risks to subjects or others occurring at another site conducting the same study that has been approved by the WFUHS IRB (external events) must be reported to the WFUHS IRB within 7 calendar days of the investigator or other members of the study team becoming aware of the event.

Any event, incident, experience, or outcome that alters the risk versus potential benefit of the research and as a result warrants a substantive change in the research protocol or informed consent process/document in order to insure the safety, rights or welfare of research subjects.

## 9.0 Correlative/Special Studies

### 9.1 Laboratory Correlative Studies

#### Biological sampling procedures

##### Immunogenicity sampling and evaluation methods

- Saliva and blood for correlative studies will be collected as described in Section 4.2.
- Blood specimens will be drawn into EDTA tubes. Samples will be labelled and transported at room temperature within one hour to [name] laboratory in Nutrition Building 2nd floor for isolation of plasma and exosomes, which will then be frozen in liq N2 for long-term storage until the completion of study.
- A portion of plasma will be submitted to [name] lab for measurement of immune micro RNA.
- A portion of the blood sample will be submitted to [name] lab for single cell RNA sequencing.

#### Saliva collection procedures

- We will target collection of 5 ml saliva from each patient.

#### Saliva Collection Recommendations

- Participants should not eat or brush their teeth within 4h prior to sample collection.
- Dental work should not be performed within 24 hours prior to sample collection.
- Saliva samples visibly contaminated with blood should be discarded and recollected. Contamination that is not visible is not of concern for this study.
- For saliva sample collection we will use 50 ml Falcon tube kept on ice. 5 mL of saliva will be collected.

#### Instructions for Collecting Saliva

1. Remove cap from tube. We will use laboratory tubes with large diameter.
2. Instruct participants to allow saliva to pool in the mouth. Some find it helpful to imagine eating their favorite food.
3. With head tilted forward, participants should drool through the SCA to collect saliva in the tube.
4. Replace cap onto tube.
5. Place label immediately.
6. Place tube in refrigerator and transport as soon as possible in an ice box.
7. Samples will be transported within one hour to [name] laboratory in Nutrition building. Saliva samples will be processed immediately after collection.

#### Proteomics

For global protein identification analysis, 10  $\mu$ L of plasma will be purified by passing through a Pierce top-2 abundant protein depletion spin column before protein extraction. Protein will be reduced and alkylated by treatment with dithiothreitol (DTT) and iodoacetamide (IAM), and then will be precipitated by adding four times the sample volume of cold acetone with incubation at -20°C. 10 ug of protein extracted from the exosome fraction will be similarly processed. Protein pellet will be air-dried at room temperature and re-suspended in 50 mM ammonium bicarbonate. 5 – 25  $\mu$ g of protein will be taken and digested with sequencing-grade modified trypsin. The peptide mixture will be acidified to quench enzyme activity and purified using a C18 desalting spin column. Peptides will be prepared in 5% (v/v)

Quad-Shot Radiotherapy in Combination with Immune Checkpoint Inhibition for Advanced/Recurrent Head and Neck Cancer  
Wake Forest Baptist Comprehensive Cancer Center  
WFBCCC60320

ACN containing 1% (v/v) formic acid and analyzed on an Orbitrap Velos Pro Mass Spectrometer (Thermo Scientific, Waltham, MA) with a Dionex Ultimate-3000 nano-UPLC system (Thermo Scientific, Waltham, MA). The LC-MS/MS system will be equipped with an Acclaim PepMap 100 (C18, 5  $\mu$ m, 100  $\text{\AA}$ , 100  $\mu$ m x 2 cm) trap column and an Acclaim PepMap RSLC (C18, 2  $\mu$ m, 100  $\text{\AA}$ , 75  $\mu$ m x 50 cm) analytical column for peptide separation. MS spectra will be acquired by data dependent scans consisting of MS/MS scans of the ten most intense ions from the full MS scan with dynamic exclusion option. To identify proteins, spectra will be searched using Sequest HT algorithm within the Proteome Discoverer v2.2 (Thermo Scientific, Waltham, MA) in combination with the UniProt protein FASTA database. Search results will contain description of identified proteins or compounds with their peak areas which represent relative abundance. Data will be exported and finalized in Microsoft Excel spreadsheet format for further statistical analysis.

#### Metabolomics

For metabolomics analysis, 50  $\mu$ L of plasma or exosome suspension spiked with an internal standard, 2-morpholinoethanesulfonic acid (MES) will be mixed with four times the sample volume of cold methanol. Supernatant will be obtained from centrifugation, which will be dried down and re-constituted in water for LC-MS/MS analysis. Sample will be analyzed on a Q Exactive HF hybrid quadrupole-Orbitrap mass spectrometer (Thermo Scientific, Waltham, MA) combined with a Vanquish UHPLC system (Thermo Scientific, Waltham, MA). Metabolites will be separated on an Ultra PFPP column (3  $\mu$ m, 2.1 mm x 150 mm, Restek, Bellefonte, PA) using a linear gradient with 100% water (mobile phase A) and 90% acetonitrile (mobile phase B) both of which equally contain 0.1% formic acid and 10mM ammonium formate. Compound Discoverer v2.1 (Thermo Scientific, Waltham, MA) will be used for metabolite annotation and relative quantification. Search results will contain description of identified compounds with their peak areas which represent relative abundance. Data will be exported and finalized in Microsoft Excel spreadsheet format for further statistical analysis.

#### Untargeted proteomics and metabolomics data processing

We will utilize an integrated mixomics data processing pipeline to align and interpret proteomic and metabolomics profiles to identify drivers of response to immunotherapy with prior quad-shot treatment. Expression of the top five candidate biomarkers identified, as determined by predictive value and fold-expression, will be secondarily validated by Western blot or mass spectrometry-based targeted analysis using standard techniques.

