### 4.2 Study Design

This is a single-arm, non-randomized pilot study to evaluate the efficacy and tolerability of combination of **two standard of care interventions** (quad-shot palliative radiotherapy and pembrolizumab immunotherapy) for patients with advanced/recurrent/metastatic head and neck cancer.

Fifteen patients will be enrolled who have no curative localized treatment options, are eligible for palliative immunotherapy (pembrolizumab), have a lesion that can be targeted by radiotherapy, and are eligible for palliative radiotherapy as recommended by their radiation oncologist.

Quad-Shot Radiotherapy in Combination with Immune Checkpoint Inhibition for  
Advanced/Recurrent Head and Neck Cancer  
Wake Forest Baptist Comprehensive Cancer Center  
WFBCCC60320

Patients eligible for this study will be those scheduled to receive palliative immunotherapy with the immune checkpoint inhibitor pembrolizumab (which is standard of care) for advanced, R/M head and neck SCC according to standard of care practice. They will also be eligible for palliative quad-shot radiotherapy according to the standard of care for advanced/recurrent/metastatic HSNCC. Quad-shot radiotherapy will be applied between immunotherapy cycle 2-3 or between immunotherapy cycle 3-4, within the last week of the cycle, and not to be delivered on the same day as ICI administration. Up to two additional quad-shot cycles will be delivered between cycles 6-7 or 7-8 (prior to cycle 8) and 11-12 or 12-13 (prior to cycle 13) of immunotherapy. The additional quad-shot treatments will be delivered in a similar fashion, in the last week of the ICI cycle.

Restaging imaging with CT, MRI or PET/CT will be obtained every 5-6 immunotherapy treatments. For the purposes of lesion measurements, follow-up imaging must be performed using the same modality (CT or MRI) as was used for initial baseline imaging. PET/CT may be utilized for follow-up imaging at the clinician's discretion. The maximum response in the targeted lesion and in the non-targeted lesions will be assessed. Subsequent immunotherapy cycles will be delivered after quad-shot radiotherapy until tumor progression or treatment intolerance.

Palliative local (non-systemic) interventions to other sites that are not quad-shot radiotherapy target sites is allowable while on study protocol treatment for the management of cancer symptoms. This should not be utilized for progression of disease at that site.

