**Single cell RNA-sequencing in blood before and after treatment.**

We propose to examine our blood samples collected before and after treatment with Pembrolizumab by single cell sequencing experiments at the Cancer Genomics Shared Resource and data analyzed by the Bioinformatics Shared Resources to determine the complex response in the immune cell populations. PBMCs from selected patients are thawed, assessed for > 70% viability, and then processed for single cell gene expression using the Next GEM Single Cell 3' GEM, Library & Gel Bead Kit v3.1 and 10X Genomics Chromium platform. Barcoded UMI-tagged libraries are sequenced on an Illumina NovaSeq 6000 targeting 4000 cells per sample at a median read depth of 50,000 reads per cell. Raw bcl and fastq data will be demultiplexed, normalized and post-processed using Cell Ranger mkfastq pipelines and QC algorithms (10X Genomics). The Cell Ranger mkfastq pipelines (10X Genomics) is used to process, QC and align sequencing reads and to optimize cell calling. Graph-based or K-means clustering algorithms implemented in Cell Ranger are applied to delineate populations of diverse immune cell lineages whose identities are frequently confirmed by the presence or absence of marker gene combinations informed by antibody-based cell sorting and identification methods, or published transcriptional signatures of FACS-sorted immune cells (42-44).

**scRNASeq data processing.** Transcript read counts will be normalized and statistically compared for differential expression between patients using DESeq2 [2] that applies the negative binomial model with independent dispersions. Differentially expressed genes (DEGs; FDR-corrected,  $p < 0.05$ ) will be analyzed by Ingenuity Pathway Analysis (IPA, [www.ingenuity.com](http://www.ingenuity.com)) and Gene Set Enrichment Analysis (GSEA) [3] to identify gene enrichment for biological processes or signaling pathways that underlie response.

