### 11.3 Power and Sample Size

Since this is a pilot study there will be no formal hypothesis tests performed. With a sample size of 15 evaluable patients (patients must be evaluable for objective response as described in Section 7.1.1), the maximum width of a 95% Clopper Pearson exact confidence interval is 0.52 (since the interval may not be symmetric this corresponds to approximately +/- 0.26 (if the response rate is as high as 7/15). If the response rate is lower than this then the width of the confidence interval will be less. With this sample size we will be able to determine whether the response rate in this treatment is high enough to warrant future examination. Based on preliminary data presented in Table 1 the response rates from previous studies is between 13 and 36% thus we would anticipate that the response rate in this study will need to be at least this high to warrant future studies.

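### Section 9.1 ranks the top five biomarkers by predictive value in about 15 patients with no stated allowance for selection, and its re-assay step can check abundance but not prediction

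*Combined protocol and SAP*

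**What the plan says.** The omics work serves the exploratory objective in Section 2.3. Section 9.1 describes an untargeted search. The proteomics text opens "For global protein identification analysis", and a metabolomics workflow follows. Both are applied to plasma and to exosomes. The profiles are then combined "to identify drivers of response to immunotherapy with prior quad-shot treatment". The selection rule reads: "Expression of the top five candidate biomarkers identified, as determined by predictive value and fold-expression, will be secondarily validated by Western blot" or by targeted mass spectrometry.

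The text does not define predictive value. It does not say which sampling time or which fraction feeds the ranking, or whose specimens are re-assayed. It states no resampling, permutation or multiplicity rule for this step. The single-cell sequencing text in the same section does name one: "Differentially expressed genes (DEGs; FDR-corrected" at 0.05.

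Section 11 covers the primary and secondary outcomes only. On size, Section 4.2 says "Fifteen patients will be enrolled" and Section 11.3 says "With a sample size of 15 evaluable patients". On the expected rate, Section 11.3 says "the response rates from previous studies is between 13 and 36" percent.

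**The concern.** A rule that takes the five highest-ranked features always returns five, whether or not any feature is related to response. When many features are searched in few patients, the winners owe much of their apparent performance to the search itself. A predictive value computed on the patients used for the ranking carries that optimism in full.

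The follow-up assay does not remove it. The protocol describes no other cohort, so the specimens available for the Western blot or targeted assay are those of the trial patients. A second assay on them asks whether the first measurement was right. The response labels are unchanged, so a chance association with response is largely carried over.

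What is at stake is the use of the result. Section 11.1 presents the pilot as information for planning further studies. Five markers with high predictive values and the word validated beside them could steer follow-on work, even if the figures are what noise would give.

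**Working it through.** **1. The protocol's own figure.** Section 11.3 says "the maximum width of a 95% Clopper Pearson exact confidence interval is 0.52", at 7/15. Beta quantiles give limits of 0.2127 and 0.7341, so the width is 0.5215, which agrees. This figure concerns the overall response rate. No size or error rate is given for the biomarker step.

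**2. Inputs.**
- From the documents: n = 15. Responders r: 0.13 × 15 = 1.95 and 0.36 × 15 = 5.4, so r is about 2 to 5.
- Assumed: m independent noise features, one value per patient, ranking by in-sample AUC taken in either direction. The protocol gives no m, so 100, 200 and 500 are shown.

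**3. Perfect separation by chance.** For one noise feature, P = 2/C(15, r). The expected number among m features is m × P.

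| r | C(15, r) | P | Expected, m = 500 |
|---|---|---|---|
| 2 | 105 | 0.0190 | 9.5 |
| 3 | 455 | 0.0044 | 2.2 |
| 4 | 1365 | 0.00147 | 0.73 |
| 5 | 3003 | 0.00067 | 0.33 |

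**4. The fifth-best noise feature.** Mean in-sample AUC by simulation, where the true AUC is 0.5 (differences of about 0.01 are simulation error):

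| r | m = 100 | m = 200 | m = 500 |
|---|---|---|---|
| 2 | 0.94 | 0.97 | 1.00 |
| 3 | 0.88 | 0.92 | 0.96 |
| 4 | 0.84 | 0.88 | 0.92 |
| 5 | 0.82 | 0.86 | 0.90 |

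**5. Chance that all five selected noise features reach AUC 0.90 or more.** This uses the exact Mann-Whitney null distribution, then the binomial probability of at least five among m.

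| r | m = 100 | m = 200 | m = 500 |
|---|---|---|---|
| 2 | 0.89 | 0.999 | 1.00 |
| 3 | 0.20 | 0.74 | 0.999 |
| 4 | 0.03 | 0.28 | 0.94 |
| 5 | 0.01 | 0.11 | 0.76 |

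**6. Re-assay against a new cohort.** Pure noise was simulated with r = 3 to 5 and m = 500 to 2,000, taking the top five by AUC and then fold difference. The correlation between assays was assumed to be 0.9.
- Mean AUC in the selecting sample: 0.93 to 0.999.
- Re-assay of the same 15 patients: 0.87 to 0.95.
- A new cohort of 15: 0.49 to 0.51.

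**7. Would FDR control serve instead?** The smallest two-sided permutation p-value for a rank statistic is 2/C(15, r). Benjamini-Hochberg at 0.05 over 500 features needs at least k features at that minimum, with k × 0.05/500 ≥ 2/C(15, r), so k ≥ 10,000 × 2/C(15, r). That is 190.5, 43.96, 14.65 and 6.66, or 191, 44, 15 and 7 features separating perfectly at once for r = 2, 3, 4 and 5. Such a gate would almost always select nothing.

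**The case against.** The strongest reply concerns the wording. The subject of the sentence is expression, and the markers are called candidates. Read closely, the Western blot is an orthogonal check of abundance, which re-assay can properly provide. A reader might infer that the protocol would confirm chance markers as drivers of response. The documents do not support that: finding drivers is the aim of the search, and nothing says that the assay establishes them. This part of the reply stands. What remains is that the word validated sits next to a ranking by predictive value and can easily be misread.

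Second, the text is silent on correction; it does not say that none will be made. The data are sent on for further statistical analysis, and the pipeline's internals are not described. This also stands. The point is under-specification, and the inflation follows only if predictive value is computed in-sample.

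Third, a reader might infer near-perfect prediction in every case. The figures do not support that either. With 100 to 200 features and 4 to 5 responders, the fifth-best noise AUC is about 0.82 to 0.88. Section 11.3 also considers 7/15; there, with 500 features, the expected number of perfect separators is 1000/6435 = 0.16 and the fifth-best AUC is about 0.885. These values are still far from 0.5. Correlated features would lower the effective number. A free choice among two fractions and at least six sampling times (Section 4.2: five infusions and the first quad-shot) would raise it.

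Fourth, a reader might infer that the FDR rule of the sequencing work should be copied here. Step 7 shows why it should not. Ranking without a significance gate is a defensible choice for an exploratory screen.

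**Conclusion.** The concern holds in limited form. As written, the rule always yields five markers from an untargeted search in about 15 patients, with no stated allowance for selection. If predictive value is in-sample, noise alone gives a fifth-best AUC of about 0.90 to 1.00 with 500 features, 0.86 to 0.97 with 200 and 0.82 to 0.94 with 100. Re-assay in the same patients would leave most of that in place.

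The size rests on an assumed feature count, independent features, one value per patient, and 2 to 5 responders. That the same patients' specimens are re-assayed is inferred from the absence of any other cohort.

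Severity is minor. The objective is exploratory, and neither the overall response rate nor any secondary endpoint depends on it.

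**What to change.** In Section 9.1, Untargeted proteomics and metabolomics data processing:

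1. Keep the top-five ranking as an exploratory screen, without an FDR gate.
2. Define predictive value, and fix in advance the sampling time and the fraction used.
3. Report predictive value only from leave-one-patient-out cross-validation, with feature selection repeated in each fold.
4. Show beside it a reference distribution from permuting the patient-level response labels through the whole pipeline. This is needed because the pooled leave-one-out AUC is biased below 0.5 under the null at this size, so 0.5 is not the right benchmark.
5. Replace validated with analytically verified in the same specimens.
6. State that prediction must be tested in an independent cohort before any marker is described as a driver of response.

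The cost is analysis code and wording; no new patients, samples or assays are needed. The downside is that reported predictive values will be lower and very imprecise. With two responders, any fold that leaves one out trains on a single responder, and the report should say so.

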#### Immune microRNA (miRs) measurements

Levels of immune-regulatory miRs will be quantified in plasma using PCR-based techniques.

miRs are important regulators of immune response miRs negatively regulate gene expression by base pairing with the 3' untranslated region of their target mRNAs. Most cellular processes, both physiological and pathological, are affected. These include differentiation, development, metabolism, proliferation, death, viral infection, and malignant transformation. Recent studies have shown that miRs play a critical role in regulating the development of immune cells and in modulating innate and adaptive immune responses. Several miRs, referred to as "immunomiRs," have been identified. miR-125b, 155, 181a, and miRs of the 17-92 complex play central roles in T-cell; miR 146a and 155, in NK cell; miR-155 and 146a, in dendritic cell; miR 125b, 146a, 155, and miRs of the 17-92 complex, in T regulatory cell; and miR-223, in myeloid derived suppressor cell development and function. Because of their low complexity (when compared to proteins), their stability, and highly sensitive detection methods, miRs are attractive biomarkers. Because of incorporation in microparticles and exosomes, miRs are stable and can be measured in blood and several other body fluids, including saliva.

Quad-Shot Radiotherapy in Combination with Immune Checkpoint Inhibition for Advanced/Recurrent Head and Neck Cancer  
Wake Forest Baptist Comprehensive Cancer Center  
WFBCCC60320

Total RNA will be isolated from plasma and saliva using the miRNeasy Mini Kit (Qiagen). Reverse transcription reactions are performed using a TaqMan MicroRNA Reverse Transcription Kit (Applied Biosystems) according to the manufacturer's instructions. qRT-PCR will be performed using the reverse transcription reaction product, TaqMan MicroRNA Assay kits, and TaqMan Universal PCR Master Mix (Applied Biosystems). Data are normalized to a *C. elegans* synthetic miR sequence, cel miR-39 (Qiagen), which is spiked in as a control during RNA isolation.

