Gamez et al.	14.8 Gy / 4	CR: 24% PR: 62%	Mucositis/xerostomia G2: 35%	1-3 cycles delivered with 3-4 weeks between cycles. Concurrent carboplatin or cetuximab administered 1 hour prior to the first fraction of each cycle.

However, the quad-shot regimen is not sufficient to provide a definitive dose for durable disease control. The equivalent dose in 2-Gy fractions (EQD2) (assuming  $\alpha/\beta=10$  [tumor]) for a single cycle is 16.9 Gy, 33.8 Gy for 2 cycles, and 50.7 Gy for 3 cycles. In prior studies, approximately

Quad-Shot Radiotherapy in Combination with Immune Checkpoint Inhibition for  
Advanced/Recurrent Head and Neck Cancer  
Wake Forest Baptist Comprehensive Cancer Center  
WFBCCC60320

64% of patients are eligible to receive more than one quad-shot cycle, and palliative response rates correlate with number of cycles delivered: 55% for 1 cycle, 44% for 2 cycles, 88% for 3 cycles (correlation coefficient 0.29, p=0.012) (18). Despite its fairly favorable rates of achieving palliation at the treated site, this palliative (rather than curative) regimen is insufficient for long-term disease control at the target site. Duration of control (DOC) has been reported in a phase II study also included in Table 2 (19). Median DOC was 5.7 months at the primary and 5.2 months at nodal sites for those with CR/PR and 1.8 months at the primary and 9.5 months at nodal sites for those with stable disease. Considering that advancements in systemic therapy using ICI have prolonged median survival for this patient cohort to 12 months or more, most patients will experience local and/or regional progression that may result in significant morbidity or even mortality. Therefore, there is strong rationale for combination therapy with PRT + immunotherapy for both patients with recurrent, advanced, incurable local disease or metastatic disease with an untreated primary.

Rationale for the Combination of Quad-Shot Radiotherapy and Immunotherapy

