#### **4.4.6 Dose Modification and Toxicity Management**

4.4.6.1 For adverse events (AEs) that are considered at least partly due to administration of pembrolizumab, the following dose adjustment guidance may be applied:

4.4.6.1.1 Treat each of the toxicities with maximum supportive care (including holding the agent suspected of causing the toxicity where required). Isolated increase in amylase has been noted after radiotherapy for the head and neck cancer, being released

Quad-Shot Radiotherapy in Combination with Immune Checkpoint Inhibition for  
Advanced/Recurrent Head and Neck Cancer  
Wake Forest Baptist Comprehensive Cancer Center  
WFBCCC60320

from the salivary glands included in the radiation field. In addition, asymptomatic increase in the lipase has been reported. If the patient does not have symptoms of pancreatitis, treatment with pembrolizumab does not need to be stopped when increase in amylase and/or lipase are identified. Follow up of the lab values until normalization is recommended.

- 4.4.6.1.2 If the symptoms promptly resolve with supportive care, consideration should be given to continuing the same dose of pembrolizumab along with appropriate continuing supportive care.
- 4.4.6.1.3 Otherwise, pembrolizumab should be permanently discontinued. Dose reductions are not permitted.

4.4.6.2 Based on the mechanism of action of pembrolizumab leading to T-cell activation and proliferation, there is the possibility of observing immune related Adverse Events (irAEs) during the conduct of this study. Potential irAEs include immune-mediated enterocolitis, dermatitis, hepatitis, and endocrinopathies. Subjects should be monitored for signs and symptoms of irAEs. In the absence of an alternate etiology (e.g., infection or PD) signs or symptoms of enterocolitis, dermatitis, hepatitis, and endocrinopathy should be considered to be immune-related.

4.4.6.3 All toxicities will be graded according to NCI CTCAE v 5.0.

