### **5.3 Exploratory Objectives**

Blood will be utilized to measure the effect of immunotherapy alone as well as in combination with quad-shot therapy on increase of the circulating immune microRNA.

In addition, blood and saliva specimens will be utilized for mechanistic investigations of the effects of quad-shot on the response to immune checkpoint inhibitors. Detailed and comprehensive single cell RNA sequencing and multi-omics analysis of both plasma and exosomes fractions will be performed.

Saliva will be utilized for metabolomics and miRNA and RNAseq analysis of oral microbiome

Quad-Shot Radiotherapy in Combination with Immune Checkpoint Inhibition for Advanced/Recurrent Head and Neck Cancer  
 Wake Forest Baptist Comprehensive Cancer Center  
 WFBCCC60320

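### Exploratory saliva microRNA is normalised only to a spike-in and collected untimed, so a change in salivary flow after quad-shot could be mistaken for a quad-shot effect

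*Combined protocol and SAP*

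**What the plan says.** **Normalisation.** Under Immune microRNA (miRs) measurements, Section 9.1 states: "Total RNA will be isolated from plasma and saliva using the miRNeasy Mini Kit (Qiagen"). Data are then normalised to a C. elegans "synthetic miR sequence, cel miR-39 (Qiagen), which is spiked in as a control during RNA isolation". No other normaliser is named.

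**Collection.** Saliva is passive drool to a set volume: "5 mL of saliva will be collected". The collection recommendations and instructions in Section 9.1 deal with eating, tooth brushing, dental work and visible blood. They do not ask for a start time, a stop time or a flow rate.

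**Timing.** Section 4.2 and footnote k of the Study Calendar (Section 6.1) call for saliva before each of the first five pembrolizumab cycles and before quad-shot. Samples are also taken around any later quad-shot. Each treated patient who continues therefore has saliva from before and after radiotherapy.

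**Use.** Section 5.3 puts blood and saliva together under mechanistic study of quad-shot, and adds: "Saliva will be utilized for metabolomics and miRNA and RNAseq analysis of oral microbiome". For the immune miRs it names blood, to "measure the effect of immunotherapy alone as well as in combination with quad-shot therapy on increase of the circulating immune microRNA". Section 9.1 agrees on the matrix: "Levels of immune-regulatory miRs will be quantified in plasma using PCR-based techniques".

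**Gland exposure.** Section 4.4.6 describes enzyme release "from the salivary glands included in the radiation field". Section 4.3.4 lists optional parotid and submandibular dose goals. Table 2 in Section 1.1 reports "Mucositis/xerostomia G2: 35" per cent in one quad-shot series.

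**The concern.** A spike-in added when RNA is isolated goes through the same losses as the sample's own RNA, so it removes differences in recovery. It carries no information about how much fluid the glands produced before the tube was filled. The normalised saliva value therefore behaves as an amount per mL.

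Because the volume target is the same at every visit, slower flow would not show in the volume. It would show only as a longer collection, and the protocol does not ask for that to be recorded.

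The protocol itself makes a flow change after quad-shot plausible. Any such change would start at the same time as the intervention, in a single-arm study. The exploratory saliva comparison before and after quad-shot could then show a shift that comes from dilution or concentration and not from immune activation, the subject of objective 2.3.1. Flow cannot be recovered later from stored samples.

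**Working it through.** The plan gives no sample size, effect size, standard deviation or analysis for saliva miR, and Section 11 does not cover the exploratory objective. There is no plan figure to reproduce, and what follows is illustrative.

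**Inputs from the documents:** spike-in as the only normaliser; 5 mL target at each visit; no recorded collection time; saliva before and after quad-shot.

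**Assumptions:** the same saliva volume and spike amount enter each isolation; flow after quad-shot is a fraction f of flow before it; miR output per minute changes by f^g. At g = 0 output does not depend on flow, and at g = 1 it falls in proportion.

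**Step 1: what the spike-in removes.** Take miR 10 units, spike 5 units and recovery e. The ratio is 10e / 5e = 2 at e = 0.4 and at e = 0.8. Double the miR concentration and it is 20e / 5e = 4 at both. Recovery cancels; concentration does not.

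**Step 2: size and direction.** Concentration is output divided by flow, so it changes by f^g / f = f^(g − 1). The qPCR shift is log2 of that, in cycles (Ct).

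| Flow after / before (f) | g = 0 | g = 0.5 | g = 1 | g = 1.2 |
|---|---|---|---|---|
| 0.80 | 1.25 (0.32 Ct) | 1.12 (0.16) | 1.00 (0) | 0.96 (−0.06) |
| 0.65 | 1.54 (0.62) | 1.24 (0.31) | 1.00 (0) | 0.92 (−0.12) |
| 0.50 | 2.00 (1.00) | 1.41 (0.50) | 1.00 (0) | 0.87 (−0.20) |

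The shift is upward if output falls less than flow, absent if they fall together, and downward if output falls faster.

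**Step 3: what timing adds.** Output per minute = concentration × volume / minutes. Assume a baseline flow of 0.5 mL/min, so 5 mL takes 10 minutes, and set baseline concentration to 1. Baseline output is 1 × 5 / 10 = 0.5.

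- Flow halves, output unchanged: 5 mL takes 20 minutes and concentration is 2. Output is 2 × 5 / 20 = 0.5, unchanged.
- Flow unchanged, true miR level doubles: 5 mL takes 10 minutes and concentration is 2. Output is 2 × 5 / 10 = 1.0, doubled.
- Flow and output both halve: 5 mL takes 20 minutes and concentration is 1. Output is 1 × 5 / 20 = 0.25, halved.

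Without timing, the first two cases give the same result, a two-fold rise. With timing they separate. The third case shows why output per minute should stand beside concentration and not replace it: it falls with gland output even when concentration does not move.

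**The case against.** **The immune-miR question belongs to blood.** Sections 5.3 and 9.1 assign the quad-shot effect on immune miRs to circulating levels measured in plasma, which salivary flow does not concentrate. A reader might infer that the flow artefact would be reported as the trial's immune effect. The documents do not support that: saliva miR has no stated contrast or decision rule, and plasma from the same visits offers a check. What remains is that Section 5.3 does put saliva under mechanistic study of quad-shot, and Section 9.1 does isolate RNA from it.

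**Direction.** A reader might infer that radiotherapy must raise saliva levels. That needs glands in the field, reduced flow at sampling, and output falling less than flow. Section 4.3.4 says the organs at risk depend on the target site, and nothing shows how output follows flow. This objection stands.

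**Frequency.** The 35% in Table 2 combines mucositis with xerostomia, in a series with concurrent carboplatin or cetuximab. It is neither a xerostomia rate nor a flow measurement, and it cannot be used to size the problem.

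**Error rates.** It is tempting to turn the shifts into false-positive rates for a paired test. Section 11.3 plans no formal tests and no standard deviation is given, so such rates would describe an analysis that is not in the plan.

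**Metabolites.** Extending the point to saliva metabolites goes too far. The Metabolomics text in Section 9.1 describes plasma and exosome suspension, and gives no saliva normalisation to assess.

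**The form.** Section 13.2 lists a specimen-tracking form whose fields are not shown. Times may already be captured there; the protocol does not require them.

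**Conclusion.** The point holds, within the exploratory saliva analysis only. With a spike-in as the sole normaliser and untimed collection, a change in saliva miR per mL across quad-shot cannot be separated from a change in flow.

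The illustrated size is a 1.25- to 2.0-fold apparent rise for flow falls of 20% to 50% if output is unchanged. It is 1.12- to 1.41-fold if output falls as the square root of flow, nil if output falls in proportion, and a fall to 0.96 to 0.87 of baseline in the g = 1.2 case. All of these rest on assumed flow losses and an assumed link between output and flow.

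The plasma immune-miR readout and the primary and secondary endpoints are not affected. The case for acting is that the missing information is nearly free to collect and cannot be reconstructed afterwards.

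**What to change.** 1. Record start time, stop time and actual volume at each saliva collection, for example on the specimen-tracking form in Section 13.2.
2. For comparisons across quad-shot, report saliva miR output per minute beside concentration, and read both against the same-visit plasma result. Keep cel-miR-39 as the extraction control.
3. State in Section 9.1 whether immune miRs are analysed in saliva as well as plasma. The text now names both for RNA isolation but only plasma for quantification.
4. A second, endogenous normaliser may be shown for saliva as a sensitivity analysis only, not as a pass/fail rule. Dividing a panel of immune miRs by their own mean would remove a genuine broad rise, and total RNA in saliva may include RNA from the oral bacteria that Section 9.1 profiles.

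The cost is two or three extra entries per saliva sample, and per-minute values that are noisier than concentrations because they also carry error in time and volume. No treatment, visit or sample-size change is needed.
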